## **12.2 ITP Bleeding Score**

Applicable period: Period I, long-term treatment of R788, Period II, non-dosing period, and Period III

The variables to be analyzed are as follows:

- Average score
- Total score
- Maximum score
- Post-dose mean of average scores (Period I, Period II)

Summary statistics will be presented for the average score, total score, and post-dose mean of average scores. For maximum score, the numbers and percentages of subjects will be presented.

## **12.3 ECOG Performance Status**

Applicable period: Period I, long-term treatment of R788, Period II, non-dosing period, Period III

The numbers and percentages of subjects with each score will be presented.

## **12.4 Laboratory and Immunoglobulin Tests**

Applicable period: Period I, long-term treatment of R788, Period II

The variables to be analyzed are listed below.

- Laboratory tests (quantitative variables)  
Hematology: Platelets, red blood cells, white blood cells, hemoglobin, hematocrit, neutrophils, eosinophils, basophils, lymphocytes, monocytes, reticulocyte ratio, MCHC, MCH, MCV  
Serum chemistry: Sodium, potassium, chloride, calcium, phosphorus, BUN, creatinine, A/G ratio, blood glucose, total protein, albumin, alanine aminotransferase (ALT), aspartate aminotransferase (AST), alkaline phosphatase (ALP), lactate dehydrogenase (LDH), gamma glutamyl transferase (gamma-GTP), total bilirubin, direct bilirubin, indirect bilirubin  
Urinalysis: Specific gravity, pH
- Laboratory tests (qualitative variables)  
Urinalysis: Glucose, ketone bodies, occult blood, protein, nitrite, bilirubin, urobilinogen, white blood cells
- Immunoglobulin test  
Immunoglobulin M (IgM), immunoglobulin G (IgG), immunoglobulin A (IgA)

### **12.4.1 Summary statistics of laboratory tests (quantitative variables) and immunoglobulin tests**

Applicable period:

Laboratory tests (quantitative variables); Period I, long-term treatment of R788, Period II, non-dosing period, Period III

Immunoglobulin test; Period I, long-term treatment of R788, Period II, non-dosing period

The variables to be analyzed are as follows:

- Laboratory tests (quantitative variables) and immunoglobulin tests
- Changes from baseline in laboratory tests (quantitative variables) and immunoglobulin tests

Summary statistics will be presented.

#### **12.4.2 Scatter plots of laboratory tests (quantitative variables) and immunoglobulin tests**

Scatter plots of quantitative variables before and after treatment will be presented.

Applicable analysis visits: Baseline, LOV

#### **12.4.3 Distribution of laboratory tests (qualitative variables)**

Applicable period: Period I, long-term treatment of R788, Period II, non-dosing period, Period III

The numbers and percentages of subjects will be presented.

#### **12.4.4 Shift tables of laboratory and immunoglobulin tests**

For measurements obtained before and after administration, the number and percentages of subjects with low, normal, or high values will be presented.

Applicable analysis visit: Baseline, LOV

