1.3.1.5 Toxicology

Toxicology studies in rats and monkeys (doses: ≤ 100 mg/kg/day of R788) for 4 to 26 weeks and 4 to 39 weeks, respectively, identified lymphohematopoietic and liver function test abnormalities (mild and fully reversible), and reproductive and/or developmental liabilities in rats and rabbits. Consistent with bone growth plate effects in rats in the general toxicity study, similar findings were observed in the carcinogenicity studies in rat and mouse and the 1-month juvenile study in rabbits (doses: 12.5 to 50 mg/kg/day). A related finding of odontodysplasia was also observed in the rat 2-year carcinogenicity study. There were no adverse effects on any male reproductive parameters in rats at doses up to 40 mg/kg/day.

There was no evidence for mutagenic or clastogenic effects in genotoxicity studies, nor carcinogenic potential in mouse and rat carcinogenicity studies. R788 promoted no remarkable adverse effects on host response in murine immunological host resistance models (*Streptococcus*, *Listeria*, and Influenza viruses).

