14.6.5 Laboratory and immunoglobulin tests

- 1) Summary statistics will be presented for quantitative values and changes from the baseline. Scatter plot of measured values before and after administration will be presented.
- 2) The number and percentage of subjects will be presented for qualitative parameters.
- 3) Shift tables before and after administration will be presented.
- 4) The maximum ALT or AST value after the start of the study treatment in each period will be categorized into $\leq 3 \times \text{ULN}$, $\geq 3 \times \text{ULN}$ to $\leq 5 \times \text{ULN}$, $\geq 5 \times \text{ULN}$ to $\leq 10 \times \text{ULN}$, and $\geq 10 \times \text{ULN}$, and frequency distribution will be presented.

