Appendix 4 Management of Neutrophil Count Decreased

Neutrophil count decreased should be managed by adjusting the dose of the study drug or performing additional tests/examinations according to the following instructions.

- 1) Neutrophil count decreased to < 1000/μL
 - (1) Repeat neutrophil count measurement immediately.
 - (2) If repeat testing confirms that neutrophil count is $<1000/\mu L$, immediately interrupt study drug administration and repeat the measurement of neutrophil count (the frequency of additional measurements will be determined by the investigator).
 - (3) When neutrophil count recovers to $> 1500/\mu$ L, restart study drug at 1 lower dose level.
- 2) Recurrence of neutrophil count of $< 1000/\mu L$
 - (1) Repeat neutrophil count measurement immediately.
 - (2) If repeat testing confirms that neutrophil count is $< 1000/\mu L$, immediately interrupt study drug administration and repeat the measurement of neutrophil count (the frequency of additional measurements will be determined by the investigator).
 - (3) When neutrophil count recovered to $> 1500/\mu L$, restart study drug at 2 lower dose level from the dose level at which the "1) Neutrophil count decreased to $< 1000/\mu L$ " occurred.

Dose Adjustment

Dose reduction				Dose before	Dose escalation		
Dose level	Dose level	Dose level	Dose level	dose	Dose	Dose	Dose
-4	-3	-2.	_1	increase/	level	level	level
-4	-3	-2	-1	reduction	+1	+2	+3
Intermention	100 mg	150 mg	100 mg	150 mg			
Interruption	qd	qd	bid	bid	_	_	
	Interruption	100 mg	150 mg	100 mg	150 mg		
		qd	qd	bid	bid		
	_	— Interruption	100 mg	150 mg	100 mg	150 mg	
			qd	qd	bid	bid	
		•	T.,.4	100 mg	150 mg	100 mg	150 mg
_			Interruption	qd	qd	bid	bid

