## 5.9 Analysis Visits

Unless otherwise specified, each analysis variable will be evaluated at the following time points.

- Data obtained outside the time window of analysis visits and data from unscheduled visits

will be excluded from summarization at each time point.

- For analyses of each treatment period, test data obtained outside the range of “the day of the last dose plus the specified number of days” will be excluded from the analysis. The specified number of days is 3 days for Period I and 7 days for Periods II and III.
- The last observed visit (LOV) other than the non-dosing period is defined as the last scheduled visit or the discontinuation visit, whichever is later, performed within the range of “the day of the last dose plus the specified number of days” for each period. The specified number of days is 3 days for Period I and 7 days for Periods II and III.
- The LOV in the non-dosing period is defined as the data for the latest test among all tests performed up to the last day of the non-dosing period.
- For all variables, Day 1 of Period I will be used as a baseline and only changes at time points after Day 1 of each period will be evaluated.
- In the non-dosing period, change from the start of the non-dosing period will be evaluated in addition to the change from Period I Day 1. Time points after Day 1 of the non-dosing period will be evaluated.

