#### **12.4.5 Distribution of post-baseline extrema of laboratory tests**

The variables to be analyzed are as follows: ULN stands for the upper limit of normal.

- ALT (post-baseline maximum):  $> 3 \times \text{ULN}$ ,  $> 5 \times \text{ULN}$ ,  $> 10 \times \text{ULN}$
- AST (post-baseline maximum):  $> 3 \times \text{ULN}$ ,  $> 5 \times \text{ULN}$ ,  $> 10 \times \text{ULN}$
- ALP (post-baseline maximum):  $> 1.5 \times \text{ULN}$
- Total bilirubin (post-baseline maximum):  $> 2 \times \text{ULN}$
- Neutrophils (post-baseline minimum):  $< 500$ ,  $500 \leq < 1000$ ,  $1000 \leq < 1500$ ,  $\geq 1500/\mu\text{L}$

The numbers and percentages of subjects will be presented.

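### Laboratory shift tables compare baseline with the last observed visit only, so a resolved abnormality can look like no change, and lymphocytes, white cells, hemoglobin and smaller liver-test rises have no worst-value subject count

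*SAP*

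**What the plan says.** Protocol 14.6.5 asks for shift tables without naming a post-dose visit: "Shift tables before and after administration will be presented". SAP 12.4.4 cross-classifies low, normal and high values and fixes the visits: "Applicable analysis visit: Baseline, LOV". The scatter plots in SAP 12.4.2 use the same two time points.

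Outside the non-dosing period, SAP 5.9 defines LOV as "the last scheduled visit or the discontinuation visit, whichever is later, performed within the range of" the last-dose day plus 3 days (Period I) or 7 days (Periods II and III). SAP 5.9 also addresses off-schedule results: "Data obtained outside the time window of analysis visits and data from unscheduled visits" are left out of the summaries at each time point.

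SAP 12.4.5 tabulates subjects by worst post-baseline value for five parameters:
- ALT and AST: above 3, 5 and 10 × ULN
- ALP: above 1.5 × ULN
- Total bilirubin: above 2 × ULN
- Neutrophils: minimum, in four categories

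Lymphocytes, white cells and hemoglobin are analysed variables in SAP 12.4 but have no row in 12.4.5.

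**The concern.** A shift table is the display a safety reader uses to see how many subjects went from normal to abnormal. When its only post-dose value is the last one, it describes where subjects ended, not what happened to them on treatment. A subject who was low at Week 6 and normal at Week 24 is counted as normal to normal.

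The SAP repairs this with worst-value rows for the five parameters in 12.4.5, but only for them and only beyond the stated thresholds. The protocol itself treats lymphocytes, white cells and hemoglobin as worth monitoring: it sets limits for all three at entry (5.2.1) and at early transition to Period II (8.3.1). The ALT/AST limit at entry and at transition, 1.5 × ULN, also lies below the lowest ALT/AST category in 12.4.5. What is at stake is a simple count by group of subjects who had such a change at any time on treatment.

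**Working it through.** The documents state no figure for this point, so there is none to reproduce. The check sets the displays side by side and then illustrates what one visit can miss.

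**1. Which display shows what**

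| SAP display | Post-baseline data used | Lymphocytes, white cells, hemoglobin | ALT/AST rise to at most 3 × ULN | Count of subjects by group |
|---|---|---|---|---|
| 12.4.4 shift table | LOV only | yes | yes | yes |
| 12.4.2 scatter plot | LOV only | yes | yes | no |
| 12.4.5 extrema | worst value | no row | below lowest category | yes, for listed rows |
| 12.4.1 summary statistics, with change from baseline | each analysis visit | yes | yes | no |
| 12.6 listing of abnormal values | per subject | yes | yes | no |
| 12.1.3 adverse events | any time on study | only if judged clinically relevant (protocol 10.15.1.3) | same condition | yes |

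For the last two clinical columns, no laboratory display combines a worst on-treatment value with a count of subjects.

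**2. Scheduled post-baseline hematology visits (SAP 5.9, Tables 5.9-1, 5.9-3 and 5.9-5)**
- Period I, Weeks 2 to 24 every 2 weeks: 24/2 = 12.
- Weeks 28 to 52 every 4 weeks: (52 − 28)/4 + 1 = 7, so long-term treatment has 12 + 7 = 19.
- Period II, after its first day: 7.

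For a subject who completes the period, the shift table uses 1 of 12, 1 of 19 or 1 of 7.

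**3. Illustration of what LOV can miss**

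Assumptions, none of them from the documents: one abnormal episode lasting m consecutive scheduled visits, its start equally likely at any of the V visits, LOV equal to the last of the V visits, and no dose change in response. The episode is still present at LOV if it starts in the last m visits, so P(missed) = 1 − m/V.

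| | m = 1 | m = 2 | m = 3 |
|---|---|---|---|
| Period I, V = 12 | 1 − 1/12 = 91.7% | 83.3% | 75.0% |
| Long-term, V = 19 | 1 − 1/19 = 94.7% | 89.5% | 84.2% |
| Period II, V = 7 | 1 − 1/7 = 85.7% | 71.4% | 57.1% |

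A shift to the worst post-baseline value would miss no measured episode. Persistent abnormalities, with m close to V, are caught by either table.

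**4. Weight of one subject**

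Planned groups are 16 and 8 (protocol 8.9.1): 1/16 = 6.25 percentage points on R788 and 1/8 = 12.5 on placebo. This is group-size arithmetic, not an estimate of incidence.

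**5. Do the dose rules bear on the uncounted parameters?**

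Protocol 8.6.2.2 names laboratory rules for ALT, AST and bilirubin (Appendix 3) and neutrophils (Appendix 4). All four have a row in 12.4.5: 4 of 4. Lymphocytes, white cells and hemoglobin have neither a named rule nor a row.

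**The case against.** Much of the opposing case is right.

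- **Dose rules.** A reader might infer that interruption and dose reduction force recovery before LOV and so hide toxicity. Appendix 4 does have sites "immediately interrupt study drug administration and repeat the measurement of neutrophil count" once a low count is confirmed. But the named laboratory rules reach only liver tests and neutrophils, whose marked worst values are counted. For lymphocytes, only the investigator's discretion over other severe or serious events could apply.
- **Recovery by the last visit.** A reader might infer that affected subjects have usually recovered by then, because the protocol says the toxicology studies "identified lymphohematopoietic and liver function test abnormalities (mild and fully reversible". Those are animal studies and do not establish recovery during continued dosing in patients. LOV is close to the last dose and may be the discontinuation visit itself, so a subject who stops for an abnormality can still show it. Appendix 3 allows restart below 1.5 × ULN, which can still be classed as high, and does not interrupt drug for an isolated bilirubin rise. Normal to normal is possible, not systematic.
- **Other displays.** A reader might infer that a lymphocyte or hemoglobin fall would have no baseline reference and no subject count anywhere. SAP 12.4.1 gives change from baseline at every visit, and 12.6 lists abnormal values per subject, which is readable with 24 planned subjects. Changes judged clinically relevant are counted as adverse events.
- **Protocol compliance.** There is no departure: 14.6.5 names no visit, and section 14 leaves detailed methods to the SAP. The SAP widened worst-value reporting beyond the protocol's ALT and AST.
- **Cut-points.** The protocol's limits are eligibility limits, not toxicity grades.

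All of this stands. It leaves one gap: a change not judged clinically relevant, in a parameter or range that 12.4.5 does not cover, and resolved by LOV, enters no count by group.

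**Conclusion.** The point holds as a minor one. The single-visit shift table can show a resolved abnormality as unchanged. The worst-value table does not cover lymphocytes, white cells, hemoglobin or smaller liver-test rises such as ALT or AST up to 3 × ULN. What is lost is a categorised subject count by group, not the data.

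Its size cannot be stated as an expected number of subjects, because the documents give no incidence for these changes on R788 in this population. The miss rates in the working depend on the assumed episode pattern and show only that one visit is a weak detector of short episodes. The tables are descriptive and do not touch the primary test. A worst-value shift is the better summary of on-treatment laboratory safety, it uses data already collected, and it stays within protocol 14.6.5.

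**What to change.** 1. In SAP 12.4.4, add a shift from baseline to the worst post-baseline value, with lowest and highest tabulated separately, for each period the section covers (Period I, long-term treatment and Period II). Keep the baseline-to-LOV table.
2. In SAP 12.4.5, add post-baseline minimum rows for lymphocytes (below 750/µL), hemoglobin (below 10 g/dL) and white cells. For white cells show both below 2500/µL and below 2000/µL, since the protocol uses the first at entry and the second at transition. Label these as tabulation cut-points taken from the protocol, not as toxicity grades or clinical rules.
3. State whether a worst value may come from an unscheduled repeat test. SAP 5.9 leaves these out of the by-visit summaries, 12.4.5 does not say, and Appendices 3 and 4 generate such repeats.
4. Record the additions and their reason in SAP section 16.

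The cost is SAP wording and a little more table programming. No new data are needed.

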#### **12.4.5 Distribution of post-baseline extrema of laboratory tests**

The variables to be analyzed are as follows: ULN stands for the upper limit of normal.

- ALT (post-baseline maximum):  $> 3 \times \text{ULN}$ ,  $> 5 \times \text{ULN}$ ,  $> 10 \times \text{ULN}$
- AST (post-baseline maximum):  $> 3 \times \text{ULN}$ ,  $> 5 \times \text{ULN}$ ,  $> 10 \times \text{ULN}$
- ALP (post-baseline maximum):  $> 1.5 \times \text{ULN}$
- Total bilirubin (post-baseline maximum):  $> 2 \times \text{ULN}$
- Neutrophils (post-baseline minimum):  $< 500$ ,  $500 \leq < 1000$ ,  $1000 \leq < 1500$ ,  $\geq 1500/\mu\text{L}$

The numbers and percentages of subjects will be presented.

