8.2 Structure of the Study

1) Screening period

Screening period is defined as 4 weeks from Screening A to before the administration of the study drug on Day 1.

2) Period I

Period I is defined as 24 weeks from after the administration of the study drug on Day 1 to Week 24.

3) Period II

- The day at the beginning of study drug administration in Period II is Week 24 for subjects who complete Period I. Period II is defined as 28 weeks from Weeks 24 to 52.
- The day at the beginning of study drug administration in Period II is ET Day 1 for early transition subjects. Period II is defined as 28 weeks from ET Day 1 to ET Week 28.

4) Non-dosing period

Non-dosing period is defined as maximum 4 weeks from Week 52 or ET Week 28 to Day 1 of Period III.

5) Period III

Period III is defined as the period from Day 1 of Period III to the date of marketing approval of R788.

6) Follow-up period

- Follow-up period is defined as 2 weeks from Week 52 or ET Week 28 to the tests at the end of the follow-up period for subjects who complete Period II and are not willing to participate in the Non-dosing period and Period III.
- Follow-up period is defined as 2 weeks from the Withdrawal Visit to the tests at the end of the follow-up period for subjects who withdraw from Period I and do not transition to Period II, those who withdraw from Period III.
- Follow-up period is defined as the period until 2 weeks after Week 52 or ET Week

28 for subjects who withdraw from the Non-dosing period before ND Week 2.

• No follow-up period is established for subjects who withdraw from the Non-dosing period at ND Week 2 or later or subjects who continue Period III until the date of marketing approval of R788.

[figure not shown]

Figure 8.2-1 Structure of Study

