12.4 Management of Abnormal Liver Function Test Values

The investigator will submit the designated form provided by the sponsor to the sponsor within 5 days after learning that all the following criteria are met at the same time. When the investigator determines the event as serious adverse event, the investigator will take actions according to "12.2 Management of Serious Adverse Events" and does not need to submit the specified form to the sponsor.

- 1) Increase in AST or ALT to $\geq 3 \times ULN$
- 2) Increase in total bilirubin to $\geq 2 \times ULN$

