Appendix 3 Management of Increases in AST, ALT, or Bilirubin

Liver enzyme abnormities or associated symptoms should be managed by adjusting the dose of the study drug or performing additional tests/examinations according to the following instructions. Additional tests/examinations may be performed at the study institution. The investigator should inform the sponsor of the onset of liver function test abnormality specified in "12.4 Management of Abnormal Liver Function Test Values" by the due date specified in "12.4 Management of Abnormal Liver Function Test Values."

R788 is an inhibitor of UGT1A1, the enzyme responsible for the glucuronidation of bilirubin; occasionally an isolated increase in total and unconjugated (indirect) bilirubin may be observed. Study drug should not be interrupted for an isolated increase in total and unconjugated (indirect) bilirubin.

- 1) In the case that subjects meet a), b) and c)
 - a) ALT or AST \geq 3 × ULN
 - b) Total bilirubin $> 2 \times ULN$
 - c) $ALP < 2 \times ULN$
 - (1) Interrupt the study drug and consider withdrawing the subject from the study due to suspected drug-induced liver injury.
 - (2) The investigator will follow the subject until liver function test results and clinical symptoms and findings return to normal or the level of Day 1, or as long as medically indicated.
 - (3) The investigator will investigate the etiology of the event and perform diagnostic examinations.
- 2) In the case that subjects meet a) or b) and have nausea, vomiting, abdominal pain
 - a) ALT or AST $\geq 3 \times ULN$
 - b) Total bilirubin $> 2 \times ULN$
 - (1) Study drug administration should be interrupted.
 - (2) Liver function tests, including bilirubin and alkaline phosphatase should be repeated until ALT/AST or total bilirubin returns to < 1.5 × ULN (the frequency of repeat tests is decided by the investigator).
 - (3) When the ALT/AST or total bilirubin returns to $< 1.5 \times ULN$, the study drug may be restarted at 1 lower dose level.
 - (4) The recurrence of the condition of 2) should be managed in the same manner.

- 3) In the case that subject meet a) or b) and subject is asymptomatic
 - a) ALT or AST $\geq 3 \times ULN$
 - b) Total bilirubin $> 2 \times ULN$
 - (1) Repeat liver function tests immediately, including ALP.
 - (2) If repeat testing shows an increase in ALT/AST or total bilirubin and the ALT/AST value exceeds 5 × ULN, immediately interrupt study drug administration.

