 - (3) Liver function tests including ALP will be repeated until ALT, AST, or total bilirubin returns to $< 1.5 \times ULN$ (the frequency of repeat tests is decided by the investigator).
 - (4) When the ALT/AST or total bilirubin returns to $< 1.5 \times ULN$, the study drug may be restarted at 1 lower dose level.
 - (5) The recurrence of the condition of 3) should be managed in the same manner.

Dose Adjustment

Dose reduction				Dose before	Dose escalation		
Dose level -4	Dose level -3	Dose level -2	Dose level	dose increase/ reduction	Dose level +1	Dose level +2	Dose level +3
Interruptio n	100 mg qd	150 mg qd	100 mg bid	150 mg bid	_	_	_
_	Interruptio n	100 mg qd	150 mg qd	100 mg bid	150 mg bid	_	_
_	_	Interruptio n	100 mg qd	150 mg qd	100 mg bid	150 mg bid	_
_	_	_	Interruptio n	100 mg qd	150 mg qd	100 mg bid	150 mg bid

References:

FDA. Guidance for Industry: Drug-induced liver injury: premarketing clinical evaluation. In: FDA,CDER,CBER.http://www.fda.gov/downloads/drugs/guidancecomplianceregulatory information/guidances/ucm174090.pdf: issued July 2009.

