## 5.4 Handling of Drug Concentration Data

Measurements below the limit of quantification (LOQ) for the plasma R406 concentration will be handled as 0 (LOQ: 2.5 ng/mL). Plasma R406 concentration data collected during interruption of R788 will be excluded from the analysis. When calculating the geometric mean and geometric CV, if the measured value before logarithmic transformation is 0, it will be handled as missing.

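### After a liver stop, samples more than 3 days (Period I) or 7 days (Period II) past the last dose enter the SAP 12.4.5 liver maxima only if the subject restarts in that period

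*SAP*

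**What the plan says.** - **The table.** SAP 12.4.5 gives numbers and percentages of subjects by post-baseline maximum: ALT and AST above 3, 5 and 10 x ULN, ALP above 1.5 x ULN and total bilirubin above 2 x ULN (the row that begins "Total bilirubin (post-baseline maximum"). SAP 12.4 runs it for Period I, long-term treatment of R788 and Period II.
- **The window.** For analyses of each treatment period, SAP 5.9 says that tests later than the last dose plus a set number of days "will be excluded from the analysis. The specified number of days is 3 days for Period I", and gives 7 days for Periods II and III. SAP 12.4.5 states no exception.
- **Stopping.** Protocol Appendix 3, item 1: "Interrupt the study drug and consider withdrawing the subject from the study due to suspected drug-induced liver injury". Item 2 also stops drug. Item 3 does so once ALT or AST exceeds 5 x ULN on repeat.
- **Off-drug testing and restart.** Item 2: "Liver function tests, including bilirubin and alkaline phosphatase should be repeated until ALT/AST or total bilirubin returns to" below 1.5 x ULN; item 3 is similar. Only then, under both items, "the study drug may be restarted at 1 lower dose level".
- **Samples taken while drug is interrupted.** The SAP removes these for one variable only (SAP 5.4): "Plasma R406 concentration data collected during interruption of R788 will be excluded from the analysis".
- **The protocol's definition.** Protocol 14.6.5 takes the highest ALT or AST value after treatment starts in each period, with no limit tied to the last dose. SAP 16.1 item 8 records new categories and added analytes for 12.4.5. Nothing in SAP section 16 records the window as a change.

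**The concern.** Whether an off-drug sample counts is settled by what happens after it is taken. If the subject recovers and restarts within the period, the last dose moves past the sample and it falls inside the range. If the subject never restarts, the last dose stays at the stop, and everything from the fourth day on (eighth in Period II) is left out. Peak liver values are thus selected by later outcome, and the samples lost belong to subjects whose course did not allow dosing to resume.

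SAP 12.4.5 is the only group table in the SAP text that counts subjects by multiples of ULN, and SAP 16.1 says its changes were made for comparison with foreign studies. A rise in transaminases that gained a bilirubin component only after the window would appear in the ALT or AST row but not in the bilirubin row. The shift table in SAP 12.4.4 does not repair this: it uses the last observed visit, which carries the same limit, and only low, normal and high categories.

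**Working it through.** The plan states no figure that depends on this rule, so there is none to reproduce. The check applies the rule to the visit schedule and to Appendix 3.

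**1. The rule.** A sample on day s counts if s ≤ L + k, where L is the day of the last dose in the period and k = 3 (Period I) or 7 (Period II). Take a stop in Period I with L = Day 57:
- No restart: Days 57 to 60 count; samples on Days 61, 64, 71 and 85 are dropped.
- Restart in Period I with last dose on, say, Day 169: all of them count.

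If dosing resumes only in Period II, the Period I table still drops them. The SAP does not spell out the long-term analysis in that case.

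**2. Scheduled visits.** Inputs are the allowance rows of the protocol schedule tables.
- Period I (Days 12–18, 26–32, and so on): consecutive visits are 26 − 18 = 8 to 32 − 12 = 20 days apart. With a last dose up to 4 days after a visit, the next visit is at least 8 − 4 = 4 days later and cannot count.
- Period II (Days 190–204, 218–232, and so on): 218 − 204 = 14 to 232 − 190 = 42 days apart, so a stop at a visit never has the next visit within 7 days.
- Follow-up (protocol 8.2): "Follow-up period is defined as 2 weeks from the Withdrawal Visit to the tests at the end of the follow-up period". With the ±7-day allowance this is 7 to 21 days after the Withdrawal Visit, so it cannot meet the 3-day limit in Period I.

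**3. What the trigger sample already counts.**

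| Stop under Appendix 3 | Already in the table | Can still be missed |
|---|---|---|
| Item 1: ALT or AST ≥ 3, bilirubin > 2, ALP < 2 x ULN | bilirubin > 2; normally ALT or AST > 3 | higher ALT/AST rows; ALP |
| Item 2: ALT or AST ≥ 3, or bilirubin > 2 x ULN, with symptoms | the row the trigger crossed | higher ALT/AST rows; whichever of bilirubin or transaminases was not the trigger; ALP |
| Item 3: no symptoms, ALT or AST > 5 x ULN on repeat | > 3 and > 5 for that enzyme | > 10; bilirubin; ALP |

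The item 3 row assumes that the repeat sample enters the maximum. SAP 5.9 excludes unscheduled data from by-time-point summaries and is silent on maxima.

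**4. Hypothetical case, R788 group of 16.** ALT is 3.5 x ULN with nausea at Week 6 (7 × 6 + 1 = Day 43). The last dose is Day 45, so the cut-off is 45 + 3 = Day 48. At Week 8 (7 × 8 + 1 = Day 57, 12 days after the last dose) ALT is 11 x ULN and bilirubin 2.5 x ULN, and no sample by Day 48 shows the rise.
- Restart later in Period I: counted in ALT > 3, > 5, > 10 and bilirubin > 2.
- Never restarted: counted in ALT > 3 only. Three cells read 0 of 16 (0%) instead of 1 of 16 (1/16 = 6.25%).

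**5. Frequency.** The documents give no rate of permanent liver stops. If 1% to 5% of R788 subjects had one (an assumption), the chance of at least one in 16 is 1 − (1 − p)^16: 1 − 0.99^16 = 15% and 1 − 0.95^16 = 56%. That is the chance of a permanent liver stop. The chance of a wrong cell is lower, because the subject must also first cross a further threshold after the window.

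**The case against.** A short on-treatment window is a legitimate choice. The steady-state half-life of R406 in protocol Table 1.3.2.1-2 is 12.3 to 16.5 hours, so 72 hours is 72/16.5 = 4.4 to 72/12.3 = 5.9 half-lives. Late samples may reflect rescue therapy or another cause. If the foreign studies used on-treatment counts, which the documents do not say, rows from all samples would be the less comparable ones. This stands, and is why the current rows should stay.

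Other outputs also show the cases. The window applies to test data, not to adverse events, which are collected to the end of follow-up and recorded at worst severity (protocol 10.15). SAP 5.3 defines a hepatic category, tabulated by severity and by drug withdrawal, and SAP 12.6 lists abnormal values by subject. A subject meeting the combined criteria of protocol 12.4 is reported to the sponsor "within 5 days after learning that all the following criteria are met at the same time", or as a serious adverse event. This stands too: the table is descriptive, and no stopping rule uses it.

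A reader might infer that the worst liver cases vanish from 12.4.5, or that suspected drug-induced liver injury goes uncounted. The table in the working shows otherwise. A reader might also infer a demonstrated bias towards R788 from the overseas figures for ALT increased (11% against 0% on placebo). Those are adverse event incidences, not permanent stops. The same protocol table shows no severe ALT or AST increase among 102 R788 subjects, and none of the treatment-related serious events listed for R788 is hepatic. The direction is plausible but not established.

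**Conclusion.** The point holds in a narrow form. As written, SAP 5.9 makes the inclusion of off-drug liver values beyond 3 or 7 days depend on a later restart within the analysed period, so 12.4.5 can undercount peaks in subjects stopped for good. A cell changes only if such a subject first crosses a further threshold after the window; each one then moves a cell by 6.3 percentage points in a group of 16. How often this would happen cannot be estimated from the documents.

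This rests on reading 5.9 as covering 12.4.5. The table shells (SAP 15) are provided separately and could not be checked. Protocol 14.6.5 points the other way for ALT and AST, so the two documents disagree on which samples define the maximum. The absence of a logged change does not show that the departure was intended: it may be an oversight in a general data rule. No case is lost from the report as a whole; the count by ULN multiple is what can be wrong. It is a cheap improvement, not a threat to the safety conclusions.

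**What to change.** Keep the present on-treatment rows in SAP 12.4.5, label them as such, and add a second set. In the second set, take each subject's extreme from all post-baseline samples up to the start of the next period or, for subjects who withdraw, up to the end-of-follow-up test. State in SAP 5.9 that the last-dose limit does not apply to these rows. State also that unscheduled and local repeat samples count, using the ULN of the laboratory that ran them. Record in SAP section 16 how both sets relate to protocol 14.6.5.

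The cost is a few sentences and extra rows in an existing table. No new data are needed: withdrawal and follow-up chemistry are already collected (protocol 11.8, 11.9), and local repeats with their reference ranges go on the case report form (protocol 10.5.2). The drawback is that late values may have causes other than the drug, so the two windows should be read side by side.
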